7.2 Enrollment

Anticipated enrollment is 1 patient every other month. We should be able to enroll 48 evaluable patients over 8 years. We anticipate 8 patients may not be evaluable such that we will have a total of 40 evaluable patients on this trial. Following enrollment of the last patient, we anticipate 6 months of follow up to obtain adequate toxicity data for the primary endpoint. Thus, we anticipate that this trial will take approximately 6-8 years to complete.

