7.4 Statistical Analysis Plan

7.4.1 Primary Clinical Endpoint: *To assess physician-reported acute grade 3 or greater gastrointestinal, genitourinary and hematologic toxicities at 12 weeks post-treatment for patients treated with linear energy transfer (LET)-optimized, intensity-modulated proton therapy (IMPT) and compare to contemporary controls treated with VMAT to determine the feasibility of this outcome for a future randomized trial.*

- At baseline, weekly during treatment, and at the 12 week post-treatment follow up appointment, the treating physician will document physician-assessed acute hematologic, gastrointestinal, genitourinary, dermatologic and other toxicities according to the Common Toxicity Criteria for Adverse Events v-4 (CTCAE v4).
- For each cumulative physician-reported toxicity (hematologic, gastrointestinal, genitourinary, dermatologic and other) at 12-weeks post-treatment, we will tabulate results by type, grade, and attribution and compare with contemporary controls treated with standard of care VMAT-based chemoradiation with 5FU and cisplatin for non-metastatic anal squamous cell carcinoma manually and individually matched for (in order): T-stage, radiation dose, age and gender. We will compare toxicity rates using a McNemar's chi-squared test for paired proportions.
- A separate PA protocol will be submitted to retrospectively review the data from these contemporary controls.
- Subset analyses will be carried out to evaluate the effect of other variables that may also impact toxicity in addition to radiation modality (IMPT vs VMAT).

On RTOG 0529, patients treated with dose-painted IMRT-based concurrent CRT for anal cancer had reported worst overall G3 or greater toxicity rates of 83%. GU/GI G3 or greater toxicity rates were 21%, dermatologic G3 or greater toxicity rates were 23% and hematologic G3 or greater toxicity rates were 58% ⁴.

To ensure an LET-optimized IMPT-based CRT approach is not overly toxic, we will monitor physician-assessed toxicity using the Bayesian optimal phase 2 (BOP2) design ²⁸. Specifically, let n denote the interim sample size and N denote the maximum sample size. Let p_{tox} denote the probability of G4 or greater toxicity and define the null hypothesis $H_0: p_{tox} > 0.5$, representing that the treatment is too toxic. We will stop enrolling patients and inspect the safety data for possible trial termination if

$$Pr(p_{tox} \leq 0.5 | data) < \lambda \left(\frac{n}{N}\right)^\alpha,$$

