where λ and α are design parameters optimized to minimize the chance of incorrectly claiming that a safe treatment is unacceptable under the alternative hypothesis $H_1: p_{tox} = 0.3$, while controlling the type I error rate at 0.1 (i.e., the chance of incorrectly claiming that an overly toxic treatment is acceptable is no more than 10%). Assuming a Beta (0.5,0.5) prior distribution for p_{tox} , the above decision rule corresponds to the following stopping boundaries:

Table 3: Optimized stopping boundaries

# patients treated	Stop if # toxicity >=
10	7
20	11
30	14
40	16

Based on Table 3, we perform the interim analysis when the number of enrolled patients reaches 10, 20, 30. When the total number of patients reaches the maximum sample size of 40, we reject the null hypothesis and conclude that the treatment is acceptable if the number of toxicities are less than 16; otherwise we conclude that the treatment is unacceptable. We anticipate we will have to enroll 48 patients to have 40 evaluable patients for this analysis.

Below in Table 4 are the operating characteristics for the safety monitoring based on 10000 simulations using the BOP2 web application, which is available at <http://www.trialdesign.org>.

Table 4: Operating characteristics

Toxicity rate	Early stopping (%)	Claim acceptable (%)	Sample size
0.5	72.70	7.31	26.7

0.4	30.55	42.83	34.9
0.3	4.93	87.57	39.1
0.2	0.17	99.57	40.0
0.1	0.00	100.00	40.0

7.4.2 Secondary Clinical Endpoints:

- Secondary Endpoint #1: *To assess the feasibility of enrolling patients on a prospective trial delivering LET-optimized IMPT for newly diagnosed, non-metastatic anal cancer.*
 - We will assess accrual at 24 months after the study open to determine feasibility of enrolling 40 patients and obtaining insurance approval for IMPT treatment over the planned 9 years.
- Secondary Endpoint #2: *To develop guidelines and workflow to create and deliver anal canal cancer treatments using LET-optimized IMPT.*
 - We will present the results of our workflows in a descriptive manner.
- Secondary Endpoint #3: *To evaluate complete response rate at 12 weeks and 24 weeks post-treatment.*
 - Complete response will be defined as no evidence of disease by physical exam, endoscopy and cross-sectional imaging.
 - Complete response will be reported at 12 and 24 weeks post-treatment as determined clinically by physical exam, endoscopic examination and imaging.

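### Low-cost improvement: pause enrolment as soon as the running G4+ toxicity count reaches the next Table 3 threshold, instead of enrolling on to the scheduled look

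*Combined protocol and SAP*

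**What the plan says.** Section 7.4.1 of the combined protocol and SAP monitors safety with a BOP2 design. The monitored quantity is defined to "denote the probability of G4 or greater toxicity". A true rate above 0.5 is too toxic, 0.3 is the safe alternative, and the design is described as "controlling the type I error rate at 0.1", where the error is accepting an overly toxic regimen.

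Table 3 gives the limits: 7 or more of 10, 11 of 20, 14 of 30, 16 of 40. On timing, "we perform the interim analysis when the number of enrolled patients reaches 10, 20, 30". At 40, fewer than 16 toxicities means acceptable. On action, the posterior rule is introduced with "We will stop enrolling patients and inspect the safety data for possible trial termination if", so an interim crossing halts enrolment and triggers an inspection. Termination is possible but not automatic.

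The documents contain no provision for acting between looks when the next limit has already been reached. Section 7.2 gives the pace: "Anticipated enrollment is 1 patient every other month".

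**The concern.** The number of patients with at least one G4+ toxicity can only rise. If the seventh such patient is patient 8, the look at 10 must cross whatever happens to patients 9 and 10. As written, those two are still enrolled.

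Such patients are exposed after the safety rule's next result is already settled, and they add nothing to that rule. Accrual is slow, so each one is also about two months during which the required inspection is deferred.

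**Working it through.** **Inputs.** Limits 7/10, 11/20, 14/30 and 16/40 (Table 3); looks at 10, 20, 30 and 40 (7.4.1); true rates 0.5 to 0.1 (Table 4); one patient per two months (7.2). Assumption for the main figures: each patient's outcome is known before the next enrolment.

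**Step 1: reproduce Table 4.** Carry the distribution of the count forward one patient at a time: P(count = c after n) = p × P(c−1 after n−1) + (1−p) × P(c after n−1). At 10, 20, 30 and 40, remove the mass at or above the limit. At p = 0.5 the removed mass is 0.1719, 0.2627, 0.2889 and 0.2028, leaving 0.0738.

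- Early stopping: 0.1719 + 0.2627 + 0.2889 = 0.7235 (0.7234 before rounding)
- Mean N: 10 × 0.1719 + 20 × 0.2627 + 30 × 0.2889 + 40 × (0.2028 + 0.0738) = 26.70

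| True rate | Table 4: early stop % / acceptable % / N | Exact |
|---|---|---|
| 0.5 | 72.70 / 7.31 / 26.7 | 72.34 / 7.38 / 26.70 |
| 0.4 | 30.55 / 42.83 / 34.9 | 30.84 / 42.81 / 34.91 |
| 0.3 | 4.93 / 87.57 / 39.1 | 5.03 / 87.50 / 39.16 |
| 0.2 | 0.17 / 99.57 / 40.0 | 0.20 / 99.58 / 39.96 |
| 0.1 | 0.00 / 100.00 / 40.0 | 0.00 / 100.00 / 40.00 |

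The differences are within the error of 10,000 simulations, so Table 4 is sound. Table 3 also follows from the stated prior and posterior rule for a range of design parameters (λ about 0.90 to 0.94).

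**Step 2: pause when the count reaches the next limit.** Use the same recursion, but remove mass after every patient: at 7 up to patient 10, 11 for patients 11-20, 14 for 21-30, 16 for 31-40. A path is removed in a block under this rule exactly when it would be removed at the end of that block under the plan's rule. The accept/reject result is therefore the same on every path.

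| True rate | Acceptable %, both rules | Mean N: plan → pause | Saving | Stopped before 40, %: plan → pause |
|---|---|---|---|---|
| 0.5 | 7.38 | 26.70 → 24.83 | 1.87 | 72.34 → 90.55 |
| 0.4 | 42.81 | 34.91 → 33.79 | 1.12 | 30.84 → 52.55 |
| 0.3 | 87.50 | 39.16 → 38.95 | 0.21 | 5.03 → 10.61 |

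**Step 3: how many patients in one trial.** At 0.5, 92.62% of trials cross some limit, so the mean saving per crossing trial is 1.87 / 0.9262 = 2.02. Of those trials, 75% enrol at least one patient after the crossing is settled, 35% at least three (six months) and 12% at least five (ten months).

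The maximum follows from the limits. A trial that obeys a look leaves it with at most one fewer than that look's limit.

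- Patients 1-10: 7 events need 7 patients; 10 − 7 = 3 spared.
- Patients 11-20: start at no more than 6, need 5 more, earliest patient 15; 5 spared.
- Patients 21-30: start at no more than 10, need 4 more, earliest patient 24; 6 spared.
- Patients 31-40: start at no more than 13, need 3 more, earliest patient 33; 7 spared, or 7 × 2 = 14 months.

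**Step 4: reporting lag.** The plan gives no reporting window for the monitored event, so the lag is an assumption. Saving at 0.5 in 200,000 simulated trials, where the zero-lag saving is 1.86:

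| Lag (patients) | Looks wait for complete data | Looks do not wait |
|---|---|---|
| 1 | 1.17 | 1.68 |
| 2 | 0.68 | 1.53 |
| 3 | 0.36 | 1.40 |

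The chance of claiming acceptability is the same in every cell.

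**Step 5: pause rule for patients 1-30 only.** Early stopping is exactly as in Step 1. The saving is 26.70 − 25.51 = 1.19 at 0.5, 0.43 at 0.4 and 0.06 at 0.3.

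**The case against.** Looks every ten patients are a legitimate BOP2 specification. The error rate is inside its 10% limit, and adverse events are also monitored throughout under 6.4.2. The average gain is small, especially at the design alternative of 0.3. At 0.5, a quarter of crossing trials would save nobody. All of this stands, and it makes the point an improvement rather than a defect.

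The immediate-outcome assumption may be generous. On-treatment grading ends within about six weeks (29 fractions, five a week), which is inside the two-month gap between enrolments. If events up to the 12 ± 4 week visit count, outcomes take about 18 weeks (6 + 12), or up to 22. That is roughly two to two and a half patients of lag, and the gain shrinks as in Step 4.

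There is also a real cost outside the safety rule. Patients not enrolled do not contribute to the matched G3+ comparison or the secondary endpoints, and even at 0.3 the chance of ending before 40 doubles. The added stops, 90.55 − 72.34 = 18.21 percentage points at 0.5 and 10.61 − 5.03 = 5.58 at 0.3, are all trials with 16 events before patient 40, which would be declared unacceptable at 40 anyway. The loss is therefore slight, but it should be acknowledged.

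A reader might make two stronger inferences. One is that a trial could have 16 events at patient 31 and treat nine more. A trial that obeys the 14/30 limit has at most 13 events at patient 30, so it cannot reach 16 before patient 33. The other is that reaching an interim limit means the trial must end. Section 7.4.1 makes the crossing certain but the consequence a halt and inspection. Only the rule at 40 gives a fixed conclusion.

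**Conclusion.** The point holds as an inexpensive safety improvement. Tables 3 and 4 are correct for the schedule they describe, but that schedule lets enrolment run on after the next crossing is settled.

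Pausing at that moment changes no accept/reject result. It saves on average 1.9 patients at a true rate of 0.5, 1.1 at 0.4 and 0.2 at 0.3, with a maximum of 7. With a lag of one to three patients the saving at 0.5 is about 0.4 to 1.7.

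The conclusion rests on two conditions. The main figures need each outcome to be known before the next enrolment. The logic needs a counted event to stay counted. Section 7.3 supports the second, since one weekly assessment makes a patient evaluable, but the substitution provision in 6.4.1 does not say what happens to an event already counted. The claim that nothing is lost applies to the safety rule only.

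**What to change.** Add to 7.4.1:

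- A running count is kept of evaluable patients with at least one G4+ toxicity.
- A counted event is not removed when a patient is substituted under 6.4.1.
- Enrolment is paused for the safety inspection already described as soon as the count reaches the next look's limit: 7 up to patient 10, 11 up to 20, 14 up to 30, 16 up to 40.

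Keep Table 3 and the final rule. Restate the early-stopping and sample-size columns of Table 4; the claim-acceptable column stands. State the assumed reporting window for the monitored event, because the size of the gain depends on it.

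If the sponsor wants to protect the number contributing to the matched comparison, apply the pause to patients 1-30 only. The early-stopping column then stands too, and only the sample-size column changes.

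The cost is a few sentences and one or two recalculated columns. CTCAE grades are already recorded weekly on treatment, so no new data collection is needed beyond keeping the tally current.

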1.0 TRIAL SUMMARY

1.1 Objectives

1.1.1 Primary objective:

1.) To assess physician-reported acute grade 3 or greater gastrointestinal, genitourinary and hematologic toxicities at 12 weeks post-treatment for patients treated with linear energy transfer (LET)-optimized, intensity-modulated proton therapy (IMPT) and compare to contemporary controls treated with VMAT to determine the feasibility of this outcome for a future randomized trial.

1.1.2 Secondary objectives:

1.) To assess the feasibility of enrolling patients on a prospective trial delivering LET-optimized IMPT for newly diagnosed, non-metastatic anal cancer.
2.) To develop guidelines and workflow to create and deliver anal canal cancer treatments using LET-optimized IMPT.
3.) To evaluate complete response rate at 12 weeks and 24 weeks post-treatment.
4.) To evaluate local progression free survival, distant metastasis-free survival and overall survival at 24 and 48 months.
5.) To evaluate rates of patient-reported acute toxicity, function, distress and QOL at 12 weeks.
6.) To evaluate rates of patient-reported late toxicity, function, distress and QOL every 6 months for 24 months.
7.) To evaluate the value of proton therapy by comparing Time-Driven Activity-Based Costing data from the date of consultation until the date of the 12-week follow up visit post-treatment with contemporary controls treated with VMAT.

1.1.3 Exploratory objectives:

1.) To compare dose to the pelvic bone marrow, bowel, bladder and genitalia between LET-optimized IMPT, traditionally-optimized IMPT and VMAT.
2.) To assess rates of leukopenia, neutropenia and lymphopenia at 12-weeks post-treatment for patients treated with LET-optimized IMPT and compare to contemporary controls treated with VMAT.
3.) To correlate white blood cell counts (WBC), absolute neutrophil counts (ANC) and absolute lymphocyte counts (ALC) with dose to the pelvic bone marrow for patients treated with LET-optimized IMPT.

Abbreviated Title	IMPT for Anal Cancer
Trial Phase	Feasibility
Clinical Indication	Newly diagnosed, non-metastatic squamous cell carcinoma of the anal canal dispositioned to definitive chemoradiation treatment
Trial Type	Treatment
Type of control	None
Route of administration	External beam proton radiation therapy with concurrent chemotherapy
Trial Blinding	NA
Treatment Groups	Single arm, non-randomized
Number of trial subjects	40
Estimated duration of trial	9 years
Duration of Participation	9 years

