2.0 TRIAL DESIGN

2.1 Research Questions

There are three main research questions we hope to answer with this study:

- 2.1.1 Is it feasible to enroll patients only a study that utilizes LET-optimized IMPT as the radiation modality in the delivery of definitive chemoradiation?
- 2.1.2 Can LET-optimized IMPT reduce biologically effective dose to the bone marrow, bladder, bowel and genitali
- 2.1.3 Can LET-optimized IMPT decrease acute and chronic gastrointestinal, genitourinary and hematologic toxicities compared to historical controls treated with VMAT?

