4.0 INCLUSION AND EXCLUSION CRITERIA

4.1 Inclusion criteria

- 1.) Histologically-proven, non-metastatic invasive primary squamous cell carcinoma of the anal canal (Stages I, II, and III).
- 2.) History/physical examination within 60 days prior to registration.
- 3.) Anal examination with biopsy on either colonoscopy, sigmoidoscopy, rigid proctoscopy or anoscopy.
- 4.) CT scan of the chest and abdomen with contrast or contrast-enhanced PET/CT scan within 60 days of registration unless the patient has a documented contrast allergy.

- 5.) CT scan of pelvis with contrast or contrast-enhanced PET/CT scan within 60 days of registration unless the patient has a documented contrast allergy.
- 6.) Zubrod Performance Status of 0-1 within 60 days prior to registration.
- 7.) Age \geq 18 years – 85 years.
- 8.) Laboratory data within 30 days prior to study registration showing:
 - Absolute neutrophil count (ANC) \geq 1.8 K/ μ L
 - Cannot be achieved through GCSF use
 - Platelets \geq 100 K/ μ L
 - Cannot be achieved through transfusion.
 - Hemoglobin \geq 8g/dL
 - Cannot be achieved through transfusion.
 - Serum creatinine \leq 1.5mg/dL
 - Bilirubin \leq 1.4mg/dL
 - Except in the case of patients with Gilberts disease.
 - White blood cells (WBC) \geq 3000/microliter
 - AST/ALT < 3x the upper limit of normal
- 9.) HIV test must be done within 90 days of study registration. If HIV positive, CD4 count must be obtained within 90 days of study registration. Note: HIV positive patients are eligible for this study if they have a CD4 count >400 cells/mm3.
- 10.) The patient must either have insurance authorization or otherwise secure funding to cover IMPT.
- 11.) The patient must be able to receive concurrent chemotherapy.

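### The 24-month accrual count cannot show how often insurance approval is obtained, because only funded patients can enroll and no record of the others is described

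*Combined protocol and SAP*

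**What the plan says.** The objective in section 1.1.2 is "To assess the feasibility of enrolling patients on a prospective trial delivering LET-optimized IMPT for newly diagnosed, non-metastatic anal cancer". Section 7.4.2 gives the whole of its analysis in one sentence: "We will assess accrual at 24 months after the study open to determine feasibility of enrolling 40 patients and obtaining insurance approval", ending "for IMPT treatment over the planned 9 years". No second variable is named, and no accrual level is attached to a conclusion.

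Section 4.1, item 10, makes funding a condition of entry: "The patient must either have insurance authorization or otherwise secure funding to cover IMPT".

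Section 7.2 gives the expected pace: "Anticipated enrollment is 1 patient every other month". It continues "We should be able to enroll 48 evaluable patients over 8 years" and then "We anticipate 8 patients may not be evaluable such that we will have a total of 40 evaluable patients on this trial". Section 7.4.1 confirms that 48 is the number to enroll and 40 the number evaluable. The trial summary lists 40 subjects and 9 years.

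The topic is not marginal to this trial. Research question 2.1.1 begins "Is it feasible to enroll patients only a study that utilizes LET-optimized IMPT", and the trial summary gives the phase as feasibility.

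**The concern.** The endpoint names two things to be judged, enrollment and insurance approval, and offers one number for both. That number counts only people who have already cleared the funding hurdle. A patient who is refused cover and has no other funding never enters the data, so the denominator for approval is missing.

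If accrual at month 24 is low, the sponsor will not know whether insurers refused, few suitable patients were seen, or patients chose otherwise. These call for different responses. If accrual is on target, the sponsor still will not know how many patients were turned away to reach it. Denials that are not written down at the time may be hard to reconstruct later.

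**Working it through.** **1. The plan's own projection.** Inputs from section 7.2: 0.5 patients per month, 8 years, 8 not evaluable.
- 0.5 × 96 months = 48 enrolled; 48 − 8 = 40 evaluable. Both figures reproduce.
- At month 24: 0.5 × 24 = 12 expected.

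**2. What the count says about approval.** Write enrolled = V × w × a, where V is the number of otherwise eligible patients, w the share willing, and a the share who obtain funding. The plan observes only the product. With values assumed for illustration, 30 × 0.5 × 0.8 = 12 and 30 × 1.0 × 0.4 = 12: the same count, with the funded share at 80% or 40%.

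Now take the simplest case. Assume that denial is the only reason for not enrolling and that all 12 enrolled through insurance. Then approval share = 12 / number seeking approval, with exact binomial 95% intervals:

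| Seeking approval | Approval share | 95% CI |
|---|---|---|
| 12 | 100% | 74–100% |
| 15 | 80% | 52–96% |
| 20 | 60% | 36–81% |
| 30 | 40% | 23–59% |
| 60 | 20% | 11–32% |

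Every row has 12 enrolled. Without the first column the share is not identified.

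**3. Whether the first column is collected elsewhere.**
- Section 6.1.1 describes eligibility screening but no log of its outcomes.
- Section 6.4.3 lists toxicities, demographics, medical history and treatment response as database content, and does not mention authorization requests or denials.
- Section 6.2.4 collects charges and cost data on enrolled patients only.
- No section says that the funding source of an enrolled patient will be recorded.

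**4. Benchmarks the documents imply.** Pace by month 24 = N × 24 / (12 × years).
- 40 in 9 years: 40 × 24 / 108 = 8.9
- 48 in 9 years: 48 × 24 / 108 = 10.7
- 48 in 8 years (section 7.2): 48 × 24 / 96 = 12

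The endpoint names 40 patients and 9 years, which points to 8.9. Section 7.2 points to 12. None is adopted as the standard.

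**5. Why a cut-off should not be set only for a low false-alarm rate.** Take accrual as Poisson (an assumption) and declare failure at 6 or fewer. This has probability 0.046 when the mean is the planned 12, which looks attractive. But 7 or 8 patients would then pass, although they project to 7 × 108 / 24 = 31.5 and 8 × 108 / 24 = 36 over 9 years, both short of 40. At half the planned rate (mean 6) the rule fires with probability 0.606, so it misses about 39% of such cases. A rule of this kind does not match the stated target.

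**The case against.** The strongest defense is that the endpoint asks a net question: can enough funded patients be enrolled? Funding is an entry condition, so denials lower the count and accrual answers that question directly. The stated objective is enrollment, no approval rate is promised, and a descriptive accrual check is common for a secondary endpoint. Much of this stands. Accrual is a fair measure of the net result. It does not stand for the second thing the sentence names, obtaining insurance approval, because the count mixes that with volume and willingness.

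Some stronger readings are tempting, and the documents do not support them:
- A reader might infer that insurance approval among enrolled patients is 100% by design. Only funding is. Criterion 10 also admits other funding, so enrollment is not proof of an insurance approval.
- A reader might infer that accrual carries no information on approval. It carries some, indirectly.
- A reader might infer that there is no benchmark at all. Benchmarks of 8.9 to 12 are implied; none is declared.
- A reader might infer that screening outcomes will be discarded. The documents are silent, and a local log may exist; it is simply not tied to this endpoint.
- A reader might infer that the accrual check is meant to plan the future randomized trial. Sections 1.1.1 and 7.4.1 link that trial to the toxicity outcome, not to this endpoint.

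**Conclusion.** The point holds in a limited form. Followed exactly, the plan will report how many funded patients enrolled by month 24. It will not give an insurance approval rate, nor the reason for a shortfall. The size of the gap can be shown only under assumptions: with denial as the sole barrier and insurance as the sole funding source, 12 enrolled fits approval anywhere from 20% to 100% as the number seeking it runs from 60 down to 12. The true number seeking approval is not in the documents.

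The undeclared benchmark is a lesser matter. Taken alone it is missing detail, but the choice between 8.9 and 12 is better made before the count is seen.

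This is a secondary, descriptive endpoint. The toxicity comparison and the safety stopping boundaries do not depend on it. The change is a cheap improvement, given weight by research question 2.1.1.

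**What to change.** Keep a prospective log with one row for each patient meeting inclusion criteria 1–9 and 11, whether or not the patient enrolls. Record whether the patient was approached and consented; whether authorization was requested, and granted or denied; the funding source; and the reason for not enrolling.

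Under Secondary Endpoint #1, report three things:
- the insurance approval rate among patients for whom it was requested, with a 95% confidence interval;
- the enrollment rate among otherwise eligible patients, with a 95% confidence interval;
- the 24-month accrual count, set against an implied pace of 8.9 (40 in 9 years), 10.7 (48 in 9 years) or 12 (48 in 8 years).

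State in advance which pace applies. If a formal cut-off is wanted, check what each passing count projects to over the full accrual period and how often the rule would miss slow accrual; 6 or fewer should not be used, for the reasons in the working.

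The cost is minor coordinator time. No extra patients, visits or changes to treatment are needed.

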- 6.3.8 Patients should be followed every 12+/-4 weeks for the first two years per the current standard of care with physical exam, labs, imaging and endoscopy at the discretion of the treating physicians (See Table 2). Only the first follow-up visit will be required on study. However, the questionnaires mentioned in 6.3.7 above will be sent via email using REDCap at 6 month intervals for voluntary participation for 24 months after treatment completion. Patients returning for follow up at MD Anderson will have their medical records queried for response rate, local progression free survival, distant metastasis-free survival and overall survival at each subsequent visit for 48 months after treatment completion.

Table 2

Time from Completion of Treatment	Evaluation	Team Providing Clinical Follow-up
3 months	PE, CT, scope	MO, XRT, CRS
6 months	PE, scope	MO + CRS*
9 months	PE	XRT
12 months	PE, CT, scope	MO + CRS
15 months	PE	XRT
18 months	PE, CT (CT not needed if <T3 or <N2)	MO
21 months	PE	XRT
24 months	PE, CT, scope	MO + CRS
30 months	PE	XRT
36 months	PE, CT, scope	MO
42 months	PE	XRT
48 months	PE, CT	MO
>48 months		Survivorship or discharge to PCP for routine care

*initial visits with CRS for proctoscopy until complete response or disease persistence is established.

PE = physical exam, CT = computed tomography, MO = medical oncology, XRT = radiation oncology, CRS = colorectal surgery, PCP = primary care physician.

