- Secondary Endpoint #4: *To evaluate local progression-free survival, distant metastasis-free survival and overall survival at 24 and 48 months.*
 - Patients will follow up with their treating physician at every 3-6 months per the current standard of care MD Anderson gastrointestinal center follow-up algorithm (Table 2).
 - Local Failure/Progression: Either recurrence of disease in the anal canal following clearance, progression of disease in the anal canal after completion of treatment or persistence of disease in the anal canal for more than 6 months after completion of treatment.
 - Distant Metastatic Failure: the appearance of distant metastatic disease.
 - Disease-Free Survival: measured as time to locoregional failure, appearance of distant metastases or death due to any cause.
 - Overall Survival: measured as time due to death due to any cause.
 - We will estimate LPFS, DMFS, and OS from time of enrollment using the Kaplan-Meier method and report estimates with appropriate 95% confidence intervals.
 - For local and regional failure, the date of failure will be recorded as 6 months after the completion of treatment in the case of persistent, biopsy-proven disease after 6 months status-post completion of all therapy.
- Secondary Endpoint #5: *To evaluate rates of patient-reported acute toxicity, function, distress and QOL at 12 weeks post-treatment.*

- PRO-CTCAE will be collected weekly during treatment and also at the 12 week post-treatment follow up visit
- EQ-5D will be collected at baseline and also at the 12 week post-treatment follow-up visit
- The EORTC QLQ- C30will be collected at baseline and also at the 12 week post-treatment followup visit
- Treatment-Related Stress Questionnaire and the Perceived Stress Scale will be collected at baseline and also at the 12 week post-treatment followup visit
- For female patients:
 - Female Sexual Function Index (FSFI)- 19 question survey validated in cancer survivors will be collected at baseline and also at the 12 week post-treatment followup visit.
- For male patients:
 - International Index of Erectile Function Questionnaire (IIEF) will be collected at baseline and also at the 12 week post-treatment followup visit

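### The local-failure and complete-response definitions leave no failure event for a patient whose stable residual anal disease is treated before 6 months and who then stays clear

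*Combined protocol and SAP*

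**What the plan says.** Section 7.4.2, Secondary Endpoint #4, gives three routes to local failure. The first two are "Either recurrence of disease in the anal canal following clearance, progression of disease in the anal canal after completion of treatment". The third is "persistence of disease in the anal canal for more than 6 months after completion of treatment". A dating rule follows: "the date of failure will be recorded as 6 months after the completion of treatment in the case of persistent, biopsy-proven disease", with the clock described as "after 6 months status-post completion of all therapy". LPFS is estimated by Kaplan-Meier from enrollment. LPFS itself is not formally defined, and no censoring rule is given.

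Secondary Endpoint #3 in the same section states: "Complete response will be defined as no evidence of disease by physical exam, endoscopy and cross-sectional imaging". It is reported at 12 and 24 weeks.

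Two places in Section 6.3 bear on early residual disease. Section 6.3.1 has the physician record residual disease at the first follow-up as a category separate from progressive disease. The footnote to Table 2 (Section 6.3.8) provides for "initial visits with CRS for proctoscopy until complete response or disease persistence is established". Neither document section says how later surgery or new anti-cancer treatment counts in any endpoint.

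**The concern.** Residual tumour that needs further treatment is normally regarded as a failure of chemoradiation to control the primary site. Under this plan such a patient can pass through follow-up without a local-failure event and can then appear disease-free because of the later treatment. The misclassification runs in one direction only, towards better local control and better response. Section 2.2 expects similar or superior tumour response, and these are the endpoints that would be read for it. If the rule is left open, each case would be classified individually in an open, single-arm study, with the outcome already known.

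**Working it through.** There is no LPFS or complete-response rate, target or power statement in the documents, so there is no figure to reproduce. The check is to run one patient through the definitions and then illustrate the size.

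**Step 1: the patient.** The first follow-up is at 12+/-4 weeks, that is, weeks 8 to 16 after chemoradiation. Six months is about 26 weeks, so 26 - 16 = 10 to 26 - 8 = 18 weeks remain before the persistence route can apply. Suppose residual tumour is found at that visit, is stable, is removed or newly treated in that interval, and the patient stays clear.

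**Step 2: the three routes.**
- Recurrence after clearance: the tumour had not cleared before the further treatment, and it does not return. Not met.
- Progression: the disease was stable. Not met.
- Persistence beyond 6 months: the disease was gone before then. Not met.

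The dating rule does not help, because it applies only to disease still present and biopsy-proven after 6 months. Its reference to all therapy also leaves unclear whether further treatment restarts the clock.

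**Step 3: complete response.** Week 24 is day 168, before 6 months (about day 183). The definition asks only for a clear exam, endoscopy and cross-sectional imaging. It has no condition on intervening treatment, so the patient qualifies if all three are done and clear. Table 2 lists exam and scope, but no CT, at 6 months. Imaging would have to come from the discretion that Section 6.3.8 gives the treating physicians.

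**Step 4: size (illustration).** The 40 is the evaluable number in Section 7.2, which is set for toxicity; the plan gives no denominator for these endpoints. Let *k* be the number of such patients and *b* the number of other local failures by the time point. Neither is in the documents; both are assumed. There is no other censoring.
- Counted as event-free: 1 - *b*/40
- Censored at the further treatment, before the other failures: 1 - *b*/(40 - *k*)
- Counted as failure: 1 - (*b* + *k*)/40

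| *b* | *k* | Event-free | Censored | Failure |
|---|---|---|---|---|
| 4 | 0 | 90.0% | 90.0% | 90.0% |
| 4 | 1 | 90.0% | 89.7% | 87.5% |
| 4 | 2 | 90.0% | 89.5% | 85.0% |
| 4 | 4 | 90.0% | 88.9% | 80.0% |
| 8 | 1 | 80.0% | 79.5% | 77.5% |
| 8 | 2 | 80.0% | 78.9% | 75.0% |
| 8 | 4 | 80.0% | 77.8% | 70.0% |

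The gap between the event-free and failure columns is *k*/40, or 2.5 points per patient. The gap between the censored and failure columns is (*k*/40) x (1 - *b*/(40 - *k*)). With *b* = 4 and *k* = 4 that is 10.0 x 0.889 = 8.9 points, so censoring removes only about a tenth of the difference. With *b* = 8 and *k* = 4 it is 7.8 of 10.0 points. For complete response, each patient scored as a responder rather than a non-responder is likewise 1/40.

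**The case against.** A reader might infer that anyone treated early for residual disease can never be a local failure, and that LPFS and response are therefore overstated. The documents do not support that. Residual disease that progresses before further treatment is a failure at once. A later recurrence in the anal canal after clearance is also a failure, although that route becomes doubtful if the canal has been removed. No text directs that the remaining patients be scored as event-free or as responders; the plan is silent, and the bias arises only if its definitions are applied as written.

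Other objections also have force. The Table 2 footnote and the 6-month rule, read together, may mean that persistence is usually called at 6 months, so early treatment could be rare or absent. The missing 6-month CT makes a recorded 24-week complete response less likely. LPFS and complete response have no test, target or planned comparison with VMAT controls. Disease-free survival is defined but is not among the planned estimates, so nothing rests on it. Counting treatment for merely suspected residual disease as failure would create the opposite bias when the specimen shows no tumour.

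All of this limits the frequency and consequence of the gap. None of it supplies a counting rule for the patient in Step 2. Choosing between an event and censoring is a choice of estimand, but the plan makes neither choice, and censoring leaves most of the difference in place.

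**Conclusion.** The point holds in a limited form. For a patient with stable residual anal disease who is treated before 6 months and then stays clear, the written definitions yield no local failure and permit a 24-week complete response. Any such patient would raise LPFS, and possibly the response rate, by up to 2.5 percentage points each. That figure assumes 40 patients, no censoring and literal application of the definitions. The number of such patients is not given, and with none there is no bias. The table shows what the handling could change; it is not an estimate of actual bias. The endpoints are secondary and untested, and the primary toxicity endpoint and the BOP2 stopping rule do not depend on them. The correction is worth making before the outcome data are analysed, but it is not critical to the trial.

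**What to change.** In Section 7.4.2, make three changes to counting. None alters patient care.

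1. Add to local failure: *Surgery or new anti-cancer treatment given for biopsy- or pathology-confirmed residual anal disease after chemoradiation is a local failure, dated at the start of that treatment.*
2. Add to complete response: *A patient who has had such treatment before the assessment is a non-responder.*
3. State that all therapy, in the dating rule, means protocol chemoradiation, so that later treatment does not restart the 6-month clock.

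Requiring confirmation keeps the rule in line with the biopsy requirement already in the dating rule and avoids counting tumour-free specimens as failures.

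The cost is a few sentences, and possibly slightly less favourable LPFS and complete-response rates. There is also some data work. Only the first follow-up visit is required on study (Section 6.3.8), and Section 6.0 allows later follow-up elsewhere, so treatment given outside the centre must be captured from forwarded records.
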